2.1 Purpose and Scope

This Primary Statistical Analysis Plan (SAP) describes the primary and secondary outcome measures and additional outcome measures of the A5360 study that will be included in the primary manuscript, and which address, at a minimum, the major primary and secondary objectives of the study. The Primary SAP outlines the general statistical approaches that will be used in the analysis of the study. It has been developed to facilitate discussion of the statistical analysis components among the study team, and to provide agreement between the study team and statisticians regarding the statistical analyses to be performed and presented in the primary analysis report. It also describes the results for the primary and secondary outcome measures that will be posted on ClinicalTrials.gov.

Detailed outlines of tables, figures, and coding descriptions that will be included in the Primary Analysis Report are included in a separate document called the Primary Analysis Implementation Plan (AIP).

Analyses for the Primary Analysis Report will be triggered by the study's primary completion date (PCD) which is defined as the date when the Sustained Virologic Response (SVR) evaluation visit has occurred for all participants enrolled. The SVR evaluation visit is the first clinic visit occurring more than 22 weeks post study entry (and up to 76 weeks post entry), where samples for HCV RNA were collected). These analyses will be finalized after all queries have been resolved.

Analyses not included in this document (i.e. those planned for manuscripts subsequent to the primary one), will be outlined in a separate, Secondary Statistical Analysis Plan, and parallel Secondary AIP.

2.2 Summary of Major Changes

Throughout this document, major updates will be in **bold** face type.

3 Study Overview

3.1 Study Design

Copied from Schema:

DESIGN

This is a phase IV open-label, multicenter, prospective study to assess the feasibility and efficacy of a minimal monitoring (MINMON) approach in active hepatitis C virus (HCV)-infected, treatment naïve participants, with and without HIV-1 co-infection, and with no cirrhosis or with compensated cirrhosis only. This study will enroll a cohort of participants with active HCV-infection to follow a minimal monitoring protocol, at US and non-US sites:

- 1) No pre-treatment HCV genotyping;
- 2) Entire treatment course (84 tablets) given to participants at entry;
- 3) No scheduled on-treatment laboratory monitoring or clinic visits;
- 4) Remote contact with participants at week 4 (adherence counseling and locator update) and week 22 (scheduling of SVR visit and locator update).
- 5) Participants will receive the fixed-dose combination (FDC) of sofosbuvir/velpatasvir (SOF/VEL) for 12 weeks.

DURATION 72 weeks

SAMPLE SIZE 400 participants

POPULATION Men and women aged 18 years or older with active HCV-infection of any genotype, HCV treatment naïve, with or without HIV-1 co-infection. Persons with either compensated cirrhosis or without evidence of cirrhosis are eligible.

STRATIFICATION The study will use stratification factors to limit enrollment by certain subgroups. These stratification factors include geographical location (limited to no more than 132 participants enrolled from sites in the US within the overall study sample), HIV-1 infection (limited to no more than 200 participants being HIV-1 positive within the overall study sample), and cirrhosis status (limited to no more than 80 participants within the overall study sample having compensated cirrhosis). There are no additional restrictions regarding participants who are both HIV-co-infected and have compensated cirrhosis, and or/geographical distribution of those participants.

3.2 Hypotheses

A MINMON strategy to deliver interferon and ribavirin (RBV)-free pan-genotypic therapy to participants with active HCV infection who are HCV treatment-naïve, globally, will be efficacious and safe.

3.3 Study Objectives

This Primary SAP addresses the following primary, secondary and selected exploratory objectives listed in the study protocol. Other study objectives in the protocol will be addressed in separate analysis plan documents.

3.3.1 Primary Objectives

1. To estimate SVR (defined as HCV RNA < lower limit of quantification [LLOQ] at least 10 weeks after the end of treatment [EOT] [which is at least 22 weeks from the study entry visit date]).
2. To summarize the occurrence of serious adverse events (SAEs) within 24 weeks following study entry.

3.3.2 Secondary Objectives

1. To estimate the proportion of participants with unplanned clinic visits prior to SVR evaluation.
2. To summarize the occurrence of adverse events, other than SAEs, within 24 weeks following study entry.
3. To estimate the proportion of participants who prematurely discontinue HCV treatment.

3.3.3 Exploratory Objectives (only the objectives addressed in the primary analysis are listed here)

1. *To describe the number and types of evaluations performed at unplanned visits.*
2. *To estimate the prevalence of HCV resistance-associated substitutions (RASs) among participants who do not achieve SVR [if data available].*

3.4 Overview of Sample Size Considerations

The sample size of 400 participants in this single-arm study was chosen for statistical properties regarding the use of efficacy data from this study to inform the utility and feasibility of future studies of the MINMON approach, and the precision (based on confidence interval (CI) width) about sustained virologic response (SVR) efficacy outcome estimates. A high benchmark is defined when the lower confidence limit of the 2-sided 95% CI about the SVR estimate is strictly greater than 96%. If a high benchmark is observed in A5360, then SVR for the MINMON strategy exceeds 96%--and future randomized clinical trials may not be needed. A low benchmark is defined as when the upper confidence limit of the 2-sided 95% CI about the SVR estimate is

strictly less than 95%. If neither benchmark is met, then it may be desirable to use the MINMON approach versus SOC in future RCT considering the efficacy estimates from this study. For additional details on sample size considerations, refer to protocol section 10.4.

3.5 Overview of Formal Interim Monitoring

Timing and triggers for reviews: The study will undergo interim review at least annually by an ACTG-appointed Study Monitoring Committee (SMC). The first interim review will occur no more than one year after the enrollment of the first study participant or approximately 6 months after 25% of the study sample (100 participants) have completed 12 weeks on study, whichever occurs earlier. An unplanned interim review will be triggered if, at any time, more than 20 persons are not evaluable for the SVR outcome before study discontinuation or 76 weeks following study enrollment. Another trigger for an unplanned interim review is if, at any time, the number of participants experiencing an SAE exceeds 5% of the interim analysis dataset, and the absolute number of participants with SAEs is at least 10. An interim review may also be convened if a concern is identified by the DAIDS clinical representative, the study chairs, or study statistician in consultation with the team.

Scope of reports: Items for SMC interim review include the following: screening and accrual, baseline characteristics of study sample, data (and specimen) completeness, premature study treatment and study discontinuation, unplanned study visits, safety (serious and other adverse events), evaliability for primary efficacy outcome, and for interim reviews including efficacy outcome: SVR outcome estimation.

Interim looks at efficacy and modification guidelines: A planned interim review for efficacy will be triggered when SVR outcomes are available for approximately 100 participants, but could occur earlier (under case of a faster than anticipated accrual rate). The team wishes that the interim look at efficacy occur while the study is still accruing, so that if SVR rate is unacceptably low (ie, futility), that there is still an opportunity to intervene before accrual to the study is completed. If the analysis sample for the initial planned review for efficacy as outlined above includes fewer than 40% participants from non-US clinical research sites, then a second planned review of efficacy will be triggered when SVR outcomes are available on approximately 230 participants (with the upper limit of US participants of 132, this estimates at least 40% non-US representation in the 2nd efficacy look interim analysis sample). The same analysis plan and monitoring bounds as defined in the first look as described below would be applied to this second look at SVR.

Consideration would be given to closer monitoring or stopping the study if there is early and strong evidence to exclude the SVR rate from being 95% or higher (ie, upper confidence bound on a 1-sided 99.9% CI is lower than 95%). With 100 participants, this boundary would be met if the observed SVR rate were 86% or lower (which corresponds to 14 or more SVR non-responders out of 100). For additional information, SVR estimates will be provided separately for subgroups such as defined by geographical location (i.e. by country), by HIV-coinfection status, and by cirrhosis status.

However, if the SMC sees early benefit of the MINMON intervention, the team intends the study to proceed with full accrual and follow-up in order to confirm early evidence, and gain precision on the efficacy outcome estimate and other outcomes.

4 Outcome Measures

Note: Information below in *italics* has been formatted according to the results format specifications in clinicaltrials.gov. All primary and secondary outcomes are anticipated to be reported with the initial results submission.

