Benchmark	Benchmark Definition (note: CI = confidence interval)	Observed conditions for meeting benchmarks given proposed sample size of 400 participants	Hypothesized true SVR rates	Probability of observing benchmark given hypothesized true SVR rate and proposed sample size	How observing different benchmarks could inform design of a future study
HIGH	Lower confidence limit of 2-sided 95% CI about SVR estimate is strictly greater than 96%	Number of participants with SVR ≥ 392 out of 400 (or conversely, 8 or fewer SVR non-responders)	96.5%	.06	A future RCT may not be needed as this benchmark implies MINMON SVR to be greater than 96%
			97%	.15	
			98%	.59	
			98.5%	.85	
LOW	Upper confidence limit of 2-sided 95% CI about the SVR estimate is strictly lower than 95%	Observed number of participants with SVR ≤ 371 out of 400 (or conversely, 29 or more SVR non-responders)	94%	.17	A future RCT may not be desired as this benchmark implies MINMON SVR to be lower than 95%.
			93%	.45	
			92%	.74	

Table 10.4-2. Probabilities of not observing either HIGH or LOW benchmark under sample size of 400 and various true SVR rates

Hypothesized True SVR rates	Probability of not observing either benchmark as defined above (i.e., observed number of SVR responders is between 372 – 391, inclusive, out of 400 participants)
90%	.023
91%	.092
92%	.264
93%	.550
94%	.829
95%	.968
96%	.978
97%	.849
98%	.407
99%	.021

Table 10.4-3 below summarizes the precision about the primary efficacy outcome of SVR (as measured by the width of the 95% CI about the SVR estimate), and location of 95% CI limits, based on various observed SVR rates and 400 individuals. The 95% confidence intervals were calculated with the binomial distribution according to the method of Wilson (Score based intervals).

Table 10.4-3. Summary of a range of observed SVR rates and their impact on the precision of the 95% CI about the observed/estimated SVR rate

Observed SVR rate among n=400	SVR 95% CI lower confidence limit	SVR 95% CI upper confidence limit	Precision of SVR estimate (95% CI width in percentages points)
90%	86.7%	92.6%	5.9
91%	87.8%	93.4%	5.6
92%	88.9%	94.3%	5.4
93%	90.1%	95.1%	5.0
94%	91.2%	95.9%	4.7
95%	92.4%	96.7%	4.3
96%	93.6%	97.5%	3.9
97%	94.8%	98.3%	3.4
98%	96.1%	99.0%	2.9
99%	97.5%	99.6%	2.2

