10.5 Data and Safety Monitoring

10.5.1 Interim Monitoring Guidelines

This study will be formally monitored at least annually by an ACTG-appointed SMC (via the standing committee for the Hepatitis TSG). The first interim review will occur no more than one year after the enrollment of the first study participant or 6 months after 25% of the study sample (100 participants) have completed 12 weeks on study, whichever occurs earlier.

A planned interim review for efficacy will be performed when SVR outcomes are available for approximately 100 participants, but could occur earlier (under case of a faster than anticipated accrual rate). The team wishes that an interim look at efficacy occur while the study is still accruing, so that if SVR rate is unacceptably low (i.e., futility), that there is still an opportunity to intervene before accrual to the study is completed.

For instance, assuming uniform accrual of 25 participants per month and SVR evaluation happening 24 weeks following study entry, the planned interim review for efficacy would occur around month 12 since study accrual commenced, with approximately 300 participants accrued, 100 participants with SVR outcome available, and 100 participants remaining to be accrued. Assuming the slower but increasing accrual rate over time and same timing of SVR evaluation, the planned interim review for efficacy would occur approximately 17 months following study opening, with approximately 265 participants accrued, 105 participants with SVR outcome, and 135 participants remaining to be accrued.

Consideration would be given to closer monitoring or stopping the study if there is early and strong evidence to exclude the SVR rate from being 95% or higher (i.e., upper confidence bound on a 1-sided 99.9% CI is lower than 95%). With 100 participants, this boundary would be met if the observed SVR rate were 86% or lower (which corresponds to 14 or more SVR non-responders out of 100). For additional information, SVR estimates will be provided separately for subgroups defined by geographical location stratification factor (ie, US versus non-US).

However, if the SMC sees early benefit of the MINMON intervention, the team intends the study to proceed with full accrual and follow-up in order to confirm early evidence, and gain precision on the efficacy outcome estimate and other

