10.6.1 Primary Efficacy Analysis

The primary efficacy outcome (SVR) will be estimated with a point-wise estimate as well as a 95%, two-sided CI. The confidence bound will be calculated with binomial distribution according to the method of Wilson (Score based interval). The impact of missingness contributing to the (lowering of the) SVR response rate will be addressed by providing the various reasons for non-SVR (e.g., discontinued treatment early due to various reasons including intolerance, HCV RNA \geq LLOQ, missing evaluation for SVR (and reasons as known), and the number of participants meeting each reason for non-SVR.

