4.1 Primary Outcome Measures

4.1.1 Primary Efficacy Outcome Measure

Measure Title: *Percentage of Participants with Sustained Virologic Response 12 (SVR12)*

Measure Description: *SVR12 was defined as plasma HCV RNA less than the lower limit of quantification (LLOQ) from the earliest sample drawn at least 22 weeks following study treatment initiation (i.e. at a visit scheduled at least 10 weeks after scheduled end of study treatment). Participants without any HCV RNA result at least 22 weeks after treatment initiation will be considered as having HCV RNA greater than the LLOQ.*

A two-sided 95%, confidence interval was calculated for this percentage using the Wilson (score) method.

Time Frame: *At least 22 weeks and up to 76 weeks from treatment initiation.*

Population Description: *Participants who enrolled and received first dose of study medication.*

Associated study objective: *“To estimate SVR (defined as HCV RNA < lower limit of quantification [LLOQ] at least 10 weeks after the end of treatment [EOT] [which is at least 22 weeks from the study entry visit date]).”*

Details: Due to the definition of SVR outcome measure, missing HCV RNA results will lower the overall percentage of participants with SVR. Therefore, various reasons for non-SVR (e.g., discontinued treatment early due to various reasons including intolerance, observed HCV RNA \geq LLOQ, missing evaluation for SVR (and reasons as known), and the number of participants meeting each reason for non-SVR, will be presented in order to interpret the overall SVR sample estimate.

For interim analyses: Interim analysis is planned when SVR outcomes are available for approximately 100 participants. At interim reviews, SVR will be calculated only among those with potential to contribute to SVR (by having at least 22 weeks elapsed since study entry). Imputation of missing SVR evaluation as non-SVR response will only occur for participants for whom more than 76 weeks since study enrollment has elapsed. In other words, early study discontinuations prior to week 22 will not be counted in SVR estimation at interim review, as these could bias the estimation of SVR towards futility. Instead, these early study discontinuations prior to week 22 (before available for SVR evaluation), and others missing SVR evaluation, will contribute to the interim monitoring

trigger. For more details, refer to Overview of Formal Interim Monitoring of section 3.5 above.

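### Is the interim futility boundary of 14 non-responders in 100 wrong because the Wilson method would give 12?

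*SAP*

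**What the plan says.** Protocol 10.5.1 and SAP 3.5 carry the same guideline. The condition in the protocol is "upper confidence bound on a 1-sided 99.9% CI is lower than 95" per cent. The SAP's worked case is "With 100 participants, this boundary would be met if the observed SVR rate were 86% or lower", followed by "which corresponds to 14 or more SVR non-responders out of 100"; the protocol prints the same rate and count. Neither section names the interval method for this bound. The consequence of crossing is that closer monitoring or stopping would be considered, so it is not an automatic stop.

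The look is planned at approximately 100 SVR outcomes; the protocol's slower-accrual example has 105. If fewer than 40% of the first-look sample is from non-US sites, a second look follows at about 230. For that look SAP 3.5 says "The same analysis plan and monitoring bounds as defined in the first look" apply, and no count is given.

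Wilson's method is named elsewhere:

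- Protocol 10.6.1, for the final two-sided 95% interval: "The confidence bound will be calculated with binomial distribution according to the method of Wilson (Score based interval".
- SAP 4.1.1, for the same SVR measure: "A two-sided 95%, confidence interval was calculated for this percentage using the Wilson (score) method".
- Protocol 10.4, for the precision table at 400 participants: "The 95% confidence intervals were calculated with the binomial distribution according to the method of Wilson (Score based intervals".

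The SAP's safety and secondary percentages also use it. SAP 4.1.1 has a paragraph on interim analyses, but it deals with who is counted and how missing results are treated, and refers back to 3.5.

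**The concern.** Wilson is the only interval method the two documents name, and SAP 4.1.1 names it for the outcome being monitored. A statistician asked for a 99.9% upper limit on SVR could reasonably reach for it. Doing so gives a boundary of 12 non-responders in 100, not the printed 14. With 12 or 13 non-responders the Wilson limit would say the boundary is met and the printed count would say it is not.

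This is the study's only efficacy boundary during accrual, and the two counts behave differently. At a true SVR of 90% the chance of crossing is 0.30 with 12 or more and 0.12 with 14 or more; at 85% it is 0.84 against 0.65. The printed count also covers exactly 100 participants, so someone must calculate the boundary for any other number, including the possible second look.

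**Working it through.** **Inputs.** One-sided level 99.9% (α = 0.001, z = 3.0902, z² = 9.5495), threshold 95%, n = 100, printed boundary 86% or 14 non-responders (Protocol 10.5.1, SAP 3.5). Let x be the number of responders and p = x/n. The boundary is the largest x whose upper limit is below 0.95.

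**Step 1: reproduce the printed figure.** The exact (Clopper-Pearson) upper limit is the 0.999 quantile of a Beta(x + 1, n − x) distribution.

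- x = 86: Beta(87, 14) gives 94.59%, below 95%, so met.
- x = 87: Beta(88, 13) gives 95.21%, not met.

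The boundary is 86 responders, or 14 non-responders, exactly as printed. The binomial tail agrees: with a true non-response rate of 5%, P(14 or more of 100) = 0.00046, below 0.001, while P(13 or more) = 0.00146, above it.

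**Step 2: the Wilson figure.** The upper limit is [p + z²/(2n) + z√(p(1 − p)/n + z²/(4n²))] / (1 + z²/n).

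At x = 88: the first two terms are 0.88 + 0.04775 = 0.92775. The root is √(0.001056 + 0.000239) = 0.03598, and times 3.0902 this is 0.11119. The sum, 1.03894, divided by 1.09550 gives 94.84%, so met. At x = 89 the limit is 95.44%, not met. The Wilson boundary is 88 responders, or 12 non-responders.

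**Step 3: where they differ at 100.**

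| Non-responders | Wilson limit | Exact limit |
|---|---|---|
| 11 | 95.44% | 96.39% |
| 12 | 94.84% | 95.81% |
| 13 | 94.21% | 95.21% |
| 14 | 93.58% | 94.59% |

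Only 12 and 13 divide the two methods.

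**Step 4: false-trigger probability at a true SVR of 95%.** From Binomial(100, 0.95): P(88 or fewer responders) = 0.0043 for the Wilson count, and P(86 or fewer) = 0.00046 for the printed count. The nominal level is 0.001. The printed rule holds it; the Wilson count exceeds it about fourfold (0.0043/0.001 = 4.3).

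**Step 5: sample sizes with no printed count.** The same search gives these minimum numbers of non-responders:

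| n | Wilson | Exact |
|---|---|---|
| 95 | 12 | 13 |
| 105 | 13 | 14 |
| 110 | 13 | 15 |
| 230 | 22 | 24 |

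At 230 the false-trigger probability at a true SVR of 95% is 0.29% for Wilson and 0.06% for exact; the chance of crossing at a true SVR of 90% is 0.62 and 0.44.

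**Step 6: the final benchmarks.** For the final benchmarks at 400 participants the plan does use Wilson: 371/400 has a two-sided 95% upper limit of 94.90%, which meets the low benchmark, whereas the exact limit of 95.09% would not. The plan therefore uses Wilson for its final intervals and, judging by the printed count, the exact method for the interim bound.

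**The case for a change.** The strongest case for a change is that the method should be fixed before data are seen. The look is at approximately 100, so the printed count may not apply to the sample that arrives, and at the possible second look there is none. An analyst who took Wilson from SAP 4.1.1 would use 22 of 230 where the exact method gives 24. The phrase about the same monitoring bounds could even be read as a literal 86%, meaning 197 or fewer responders of 230 and so 33 or more non-responders. One sentence and a short table would remove the doubt at almost no cost.

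Some of this stands. The method is not named in either document, Wilson is the only one that is, and a reader who imports it will not reproduce 86%.

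It does not amount to an error or a contradiction. Where a count is printed, it settles the matter: 12 or 13 non-responders in 100 do not meet the boundary, and the count itself shows that Wilson was not used. For other sample sizes the natural course is the method that returns the printed number. The literal 86% reading is strained, because both documents define the boundary by the confidence limit and give 86% only as its value at 100. The protocol also refers to a Study Monitoring Plan for further detail (7.4 and 10.5.1); it is not among the documents here, so the method may be stated there.

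**Conclusion.** The printed boundary is correct and needs no revision. It is the exact binomial boundary for a one-sided 99.9% upper limit below 95%, it is the same in both documents, and its false-trigger probability of 0.046% at a true SVR of 95% respects the stated level. Moving it to 88% and 12 non-responders would raise that probability to 0.43%, so the rule would no longer have the property it claims.

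The remaining gap is an unnamed interval method. It shifts the boundary by one or two non-responders at sample sizes near 100 (from 95 to 110) and by two at 230, and the look at 230 happens only if the first-look sample has fewer than 40% non-US participants. The guideline asks only that closer monitoring or stopping be considered, and the committee also sees the SVR estimates, safety data and evaluability. A competent analyst fills this gap by carrying the exact method forward.

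This rests on two assumptions: that the printed count shows the intended method, which its exact reproduction supports, and that the committee treats the boundary as advisory, as both documents say.
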